BACKGROUND ON RADIOLOGICALLY ISOLATED SYNDROME

The term ‘radiologically isolated syndrome’ (RIS) was first introduced in 2009 by Okuda and colleagues to describe the presence of these incidentally identified CNS white matter anomalies that were typical of inflammatory demyelinating disease in subjects with no present or past symptoms suggestive of MS (Okuda et al. 2009). The diagnostic criteria for RIS proposed by Okuda et al. requires a heavy lesion burden, strictly defining the morphology, size, location, number, and distribution of lesions fulfilling at least three out of four Barkhoff criteria for dissemination in space (DIS) in order to differentiate those at highest-risk for developing MS (Table 1). In addition, the Okuda criteria also include an indication for MRI other than suspected MS, and exclude other disease entities that could better account for the observed paraclinical anomalies. Approximately one-third of patients with RIS will experience a first acute or progressive clinical event related to CNS demyelination within 5 years, while two-thirds of patients with RIS show radiologic progression with a median of 2.7 years (Lebrun et al. 2008; Granberg et al 2013; Okuda et al. 2014, and Yamout 2017). Several factors have been associated with conversion to MS in RIS patients, including younger age (<40), sex (male) and the presence of spinal cord or infratentorial brain lesions (Okuda et al. 2011; Etemadifar et al. 2014; Okuda et al. 2014; Makhani 2017; Thouvenot et al. 2019). Abnormal cerebrospinal fluid (CSF) findings, including the presence of oligoclonal bands (OCBs) and/or elevated IgG index, have also been suggested as potential risk factors for clinical conversion (Nakamura et al. 2014; Gastaldi 2017; Matute-Blanch et al. 2018; and Makhani et al. 2019).

Table 1 Diagnostic Criteria for Dissemination in Space

Okuda Diagnostic Criteria for RIS	2017 McDonald Diagnostic Criteria for MS
The presence of incidentally identified CNS white matter anomalies meeting the following MRI criteria:	≥1 T2-hyperintense lesions characteristic of MS in ≥2 of 4 CNS areas Periventricular Cortical or juxtacortical Infratentorial brain regions

Ovoid, well-circumscribed, and homogeneous foci with or without involvement of the corpus callosum T2 hyperintensities measuring >3mm and fulfilling ≥3 of 4 Barkhof criteria for DIS ≥9 lesions or ≥1 Gd+ lesion ≥3 periventricular lesions ≥1 juxtacortical lesion ≥1 infratentorial lesion	Spinal cord
--	-------------

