Appendix 2. For the sub-study schema, please refer to **Appendix 3**

This is a multicenter, randomized, double-blind, placebo-controlled, Phase 4 study in which eligible patients with RIS (as defined by meeting 2017 McDonald criteria for DIS) will be randomized 1:1 to receive ocrelizumab treatment or placebo (standard of care). Three courses of ocrelizumab or placebo will be administered over the course of the study. The first course of ocrelizumab will be administered as two 300 mg infusions at Week 0 (Day 1) and Week 2 (Day 15), with the subsequent second- and third-courses given as a single 600 mg infusion at Weeks 24 and 48. Placebo will be administered at the same timepoints. Screening will occur over a 45-day period.

All participants must have had CSF analysis at baseline. For those who have had lumbar puncture and CSF analysis prior to screening for this study, historical results (for oligoclonal banding) will be accepted as long as original source documentation can be provided. Optional CSF (baseline, weeks 104 and 208, with paired blood) can still be contributed to the study. For those who have not had prior CSF analysis, lumbar puncture and CSF analysis will be required at baseline with two optional follow-up lumbar punctures post-baseline (Weeks 104 and 208). Refer to Figure 1 Study Schema.

The double-blind phase will be considered complete when the results of the primary analysis are disclosed and the study becomes unblinded to sites. If the projected number of radiological or clinical events (21) has not been reached when the last patient completes 4 years in the double-blind phase because of slower than anticipated event rates, the double-blind phase may be extended until the required number of events have occurred. After the primary analysis is complete, patients will remain in the study and be followed for a minimum total of 3 years after treatment.

As the primary analysis is event driven, the study duration in the double-blind phase will vary for each patient.

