The purpose of this study is estimation and hypothesis testing regarding the effect of ocrelizumab on the time from baseline to radiological or clinical evidence of MS relative to placebo. P-values, point- and interval estimates of the true underlying hazard ratio will be obtained.

The sample size of this trial is based on testing the null hypothesis of no difference between the control and ocrelizumab arms. This study will enroll approximately 100 patients with an expected recruitment of over 2 years. The sample size of this study is driven by the primary efficacy analysis of radiological or clinical evidence of MS and the following assumptions:

A two-group test of equal times to radiological or clinical evidence of MS

Two-sided type I error = 0.05

33% of the patients in the control arm and 20% of patients in the ocrelizumab arm having radiological or clinical evidence of MS occurring by 4 years.

A final analysis is based on approximately 21 radiological or clinical events to have 80% power 10% annual dropout rate.

SUMMARIES OF CONDUCT OF STUDY

The number of patients who enroll, discontinue, or complete the study and ocrelizumab administration will be summarized. Reasons for premature study discontinuation and treatment discontinuation will be listed and summarized. Major protocol deviations, including violations of inclusion/exclusion criteria will also be listed and summarized.

SUMMARIES OF TREATMENT GROUP COMPARABILITY

Demographic and baseline characteristics (including age, sex, body mass index), medical history, and neurological examination will be summarized using means, standard deviations, medians, and ranges for continuous variables and proportions for categorical variables, as appropriate. MS disease history (duration since MS first symptom, duration since MS diagnosis), MS disease status (MS treatment naïve or experienced) will be summarized. The baseline measures of MRI, EDSS, or other important endpoints will also be tabulated. Summaries will be presented overall and by patient cohorts.

EFFICACY ANALYSES

The primary efficacy analysis population will consist of all randomized patients, with patients grouped according to their assigned treatment (i.e., the ITT population). All statistical hypotheses for the primary and secondary endpoints and treatment comparisons will be tested at the 5% significance level against two-sided alternative unless otherwise specified.

Primary Efficacy Endpoint

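### The 33% four-year control rate for the composite endpoint has no source and sits below the document's own radiologic figure; separately, 21 events give about 27% power, not 80%, and can trigger early unblinding.

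*Combined protocol and SAP*

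**What the plan says.** Section 6.1 (Determination of Sample Size) lists these assumptions:

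- Size and accrual: "This study will enroll approximately 100 patients with an expected recruitment of over 2 years".
- Test level: "Two-sided type I error = 0.05".
- Event rates, with a 4-year horizon: "33% of the patients in the control arm and 20% of patients in the ocrelizumab arm having radiological or clinical evidence of MS".
- Events, power and dropout: "A final analysis is based on approximately 21 radiological or clinical events to have 80% power 10% annual dropout rate".

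Section 6.4.1 counts as an event the first new gadolinium-enhancing lesion, new or enlarging T2 lesion, or clinical demyelinating event.

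The Background on Radiologically Isolated Syndrome gives two figures. For clinical events: "Approximately one-third of patients with RIS will experience a first acute or progressive clinical event related to CNS demyelination within 5 years". For imaging: "two-thirds of patients with RIS show radiologic progression with a median of 2.7 years".

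Three places govern when the analysis and unblinding happen:

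- Section 3.1 allows the blinded phase to be extended: "If the projected number of radiological or clinical events (21) has not been reached when the last patient completes 4 years".
- The opening of Section 6 puts the primary analysis at the point where the last patient has reached 4 years and the event count has also been met.
- Appendix 1, footnote v, says that if the required events accrue across the study before the 3-year follow-up minimum, patients will be unblinded and then followed.

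**The concern.** A composite that includes any new lesion cannot have a lower event rate than its radiologic component. Yet the composite rate in Section 6.1 is close to the Background's clinical-only figure and well below its radiologic figure, and nothing in the document explains the gap.

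The target of 21 events and its expected date both depend on that rate. If the true rate is higher, 21 events arrive early. The extension rule and the blinded check on event numbers would then be satisfied with little information in hand, and footnote v would open the blind while many patients have short follow-up.

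Section 6.1 also presents 21 as the count that delivers 80% power, so this figure has to be checked against the plan's own rates before it serves as a trigger.

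**Working it through.** **Inputs.** From Section 6.1: control 33% and ocrelizumab 20% at 4 years, two-sided 0.05, 21 events, 80% power, 10% annual dropout, about 100 patients over about 2 years. From Section 3.1: 1:1 allocation. My assumptions: 50 per arm, exponential event and dropout times, uniform 2-year accrual.

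**1. The plan's own figures.**

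- HR = ln(0.80)/ln(0.67) = 0.557, so |ln HR| = 0.585.
- Events for 80% power (Schoenfeld) = 4(1.960 + 0.842)²/0.585² ≈ 92. Freedman's formula gives 98, and a one-sided Schoenfeld calculation gives 73.
- Power at 21 events = Φ(½√21 × 0.585 − 1.960) = Φ(−0.62) = 26.8%.
- As two proportions with 50 per arm, power is 31%.
- For 21 events to give 80% power, HR must be about 0.29, for example 33% against about 11%.

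No variant tried reproduces 80% at 21 events.

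**2. Where 21 probably comes from.** The yearly hazards are λc = −ln(0.67)/4 = 0.100 (control), λt = 0.056 (ocrelizumab) and η = −ln(0.9) = 0.105 (dropout). The chance of an observed event in 4 years is λ/(λ+η) × [1 − exp(−4(λ+η))], which is 0.273 for control and 0.164 for ocrelizumab. Expected events = 50 × 0.273 + 50 × 0.164 = 21.9. So 21 reproduces, to within one event, as an expected yield and not as a power requirement.

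**3. What the Background implies for controls at 4 years.**

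- Clinical only, one-third by 5 years: 1 − (2/3)^(4/5) = 27.7%. A composite rate of 33% leaves about 5 percentage points for patients with a radiologic event only.
- Radiologic, two-thirds ever progress with median 2.7 years among them: (2/3)(1 − 0.5^(4/2.7)) = 43%.
- Radiologic, two-thirds by 5 years: 1 − (1/3)^(4/5) = 59% (58.5% before rounding).
- Radiologic, median 2.7 years in all patients: 1 − 0.5^(4/2.7) = 64%.
- Radiologic, two-thirds by 2.7 years: 1 − (1/3)^(4/2.7) = 80%.

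Every radiologic reading exceeds 33%, and clinical events can only add to it.

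**4. Events, timing and power with HR held at 0.557.** Each cell gives expected events, power, and the HR detectable with 80% power, exp(−2 × 2.802/√events).

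| Control rate | 4 years per patient | All followed until last patient reaches 4 years | 21st event, years from first enrolment |
|---|---|---|---|
| 33% | 22; 28%; 0.30 | 25; 31%; 0.33 | 4.8 to 5.1 |
| 43% | 29; 35%; 0.35 | 33; 39%; 0.38 | 3.6 |
| 64% | 45; 50%; 0.43 | 50; 54%; 0.45 | 2.3 |

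In the first row, 5.1 applies if follow-up stops at 4 years per patient and 4.8 if it continues. At 64% the 21st event falls about four months after enrolment closes (2.34 − 2 = 0.34 year). These are occurrence times; lesions are only seen at scheduled scans, so recorded dates would be somewhat later.

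**5. If the ocrelizumab arm is held at 20% instead.** HR becomes 0.40 at a 43% control rate and 0.22 at 64%, and 80% power needs 38 and 14 events. The power statement cannot be repaired without saying which effect is assumed.

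**The case against.** The case for the plan has real force, and four stronger readings go beyond the documents.

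- **A reader might infer that 33% is wrong.** This is not shown. The radiologic sentence can be read several ways, its sources are not available here, and progression is not defined in it. The Background says the older diagnostic criteria demand a heavier lesion burden than this trial's entry criterion, and relatives found by pre-screening may also differ, so the true rate could be lower than 43%. Against that, patients radiologically stable for 5 years or more are excluded, and brain and cervical cord MRI is frequent. The document weighs none of this.
- **A reader might infer that 33% is simply the clinical figure reused.** The numbers match but the horizons do not: one is at 5 years, the other at 4. The document does not say how 33% was chosen.
- **A reader might blame the power shortfall on the control rate.** At a fixed hazard ratio, the required 92 events and the 27% at 21 events do not depend on it. A higher rate would yield more events and more power by year 4, so on that count the inconsistency errs in the trial's favour.
- **A reader might infer that events beyond 21 would be discarded.** Section 6 requires 4 years for the last patient as well as the count, and Section 6.4.1 follows patients until the primary analysis, so later events would be counted under those rules. The conflict with footnote v exists whatever the rate; a higher rate makes it more likely to arise.

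What remains is an unsourced rate that disagrees with the Background, a power figure that fails on its own inputs, and two incompatible rules on when the blind is opened.

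**Conclusion.** The point holds as three linked but distinct findings.

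1. The composite control rate is unexplained, and it lies below every reading tried of the document's radiologic figure (33% against 43% to 80%). It needs a justification; it has not been refuted.
2. The stated 80% power is wrong on the plan's own rates. It is about 27% at 21 events, and about 92 events would be needed. This rests only on 33% against 20%, proportional hazards and a two-sided 0.05 test.
3. With a control rate of 43–64% and HR 0.557, 21 events accrue about 1.5 to 2.5 years sooner than at 33%. Footnote v would then open the blind before the point that Section 6 sets for the analysis. This rests on the accrual, dropout and exponential assumptions above.

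The second finding is certain from the text. The first and third are conditional on how the Background figure is read and on whether its cohorts resemble this trial's patients.

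**What to change.** 1. In Section 6.1, give the source of the composite control rate, or re-derive it for this population and endpoint, and say why it differs from the Background.
2. Report expected events and required events as separate quantities. Replace the 80% claim with the actual power, or with the detectable hazard ratio, for the follow-up rule chosen. With 4 years per patient, that is about 22 events (28% power, HR 0.30) at a 33% control rate and 29–45 events (35–50%, HR 0.35–0.43) at 43–64%. With everyone followed until the last patient reaches 4 years, it is about 25 events (31%, HR 0.33) and 33–50 events (39–54%, HR 0.38–0.45).
3. Reconcile Section 3.1, the opening of Section 6 and Appendix 1 footnote v. The primary analysis and unblinding should take place when the last patient reaches 4 years, using all events to that date. Keep 21 only as a minimum that can extend the blinded phase but cannot shorten it.

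The cost is a rewritten sample-size paragraph, consistent trigger wording and a less favourable stated power. No patients are added. The changes should be made before any unblinding.

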The Parties shall follow their own procedures for adherence to AE reporting timelines.

Each Party shall monitor and, as applicable, request feedback from the other Party regarding AE report timeliness in accordance with its own procedures. The Parties agree to provide written responses in a timely manner to inquiries from the other Party regarding AE reports received outside the agreed upon Agreement timelines. If there is any detection of trends of increasing or persistent non-compliance to transmission timelines stipulated in this Agreement, both Parties agree to conduct ad hoc or institute a regular joint meeting to address the issue.

In case of concerns related to non-compliance of processes, other than exchange timelines, with this Agreement, the Parties will jointly discuss and collaborate on

clarifying and resolving the issues causing non-compliance. Every effort will be made by the non-compliant Party to solve the non-compliance issues and inform the other Party of the corrective and preventative actions taken.

Upon justified request, given sufficient notice of no less than sixty (60) calendar days, an audit under the provisions of this Agreement can be requested by either Party. The Parties will then discuss and agree in good faith upon the audit scope, agenda and execution of the audit. The requesting Party will bear the cost of the audit.

STATISTICAL CONSIDERATIONS

Unless otherwise specified, all baseline and efficacy analyses will be based on the intend-to-treat (ITT) population (defined as all randomized patients). The safety evaluable population will include all patients who received any amount of study drug. Unless otherwise specified, all baseline and efficacy analyses will use the ITT population as assigned by randomization. Safety analyses will be performed by treatment received.

The primary analysis will occur when the last randomized patient has reached 4 years and the specified number of new radiological or clinical evidence of MS has accrued as specified in Section 3.1.

All statistical hypotheses for the primary and secondary endpoints and treatment comparisons will be tested at the 5% significance level ($\alpha = 0.05$) against two-sided alternatives unless otherwise specified. The SAP will contain full details of the statistical analyses specified for this protocol.

DETERMINATION OF SAMPLE SIZE

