All verbatim adverse event terms will be mapped to MedDRA thesaurus terms, and adverse event severity will be graded according to CTCAE v5.0 grade. All adverse events, serious adverse events, adverse events leading to death, adverse events of special interest, and adverse events leading to study treatment discontinuation that occur on or after the first dose of study treatment (i.e., treatment-emergent adverse events) will be summarized by mapped term, appropriate thesaurus level, and severity grade. For events of varying severity, the highest grade will be used in the summaries. Deaths and cause of death will be summarized.

Associated laboratory parameters, such as hepatic function, renal function, and hematology values, will be grouped and presented together. Marked abnormalities will also be flagged.

BIOMARKER ANALYSES

Biomarkers will be assessed at baseline (screening) and subsequent time points following administration of ocrelizumab or placebo. Biomarkers levels at baseline or over time may be compared with efficacy or safety measurements to assess prognostic or

predictive properties. Biomarkers may also be analyzed over time as absolute values and/or percent change relative to baseline over time, and may be compared with efficacy, other biomarkers, or safety measurements.

INTERIM ANALYSES

The iDMC will review interim analyses as specified in the iDMC Charter. Interim analyses will be conducted by the unblinded statistician(s) and will focus on recruitment/enrollment, study conduct and safety.

No formal interim analyses for futility or efficacy are planned. However, the aggregate rate of the primary outcome will be monitored throughout the study to assure a sufficient number of events. The following scenario may trigger an interim look for futility.

If we are not on target to reach the hypothesized number of events (in the blinded dataset) by the end of the follow-up period, we will assess whether an extension to follow-up is fiscally feasible. If follow-up is feasible, a non-binding futility analysis using an alpha-spending function will be conducted to determine whether it is worth extending follow-up.

Similarly, we will monitor the current trend of treatment in this patient population. The following scenario may trigger an interim look for efficacy if applicable.

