^q All MRIs will be read by a central reading center. Prior to initiation of study drug a QC report for the Screening MRI scan must have been received from the centralized reading center confirming scan passed QC. The brain MRI requires at least 2 business days from scan receipt to be quality checked before dosing of study drug. Screening MRIs must also be confirmed by the central MRI reader to meet 2017 McDonald criteria for dissemination in space prior to patient randomization. Contrast agent (gadolinium) required only at screening MRI and annually (Weeks 48, 104, 156, and 208).

^r To be obtained/Performed optionally, at the Investigators discretion, in case of neurologic event or suspected neurologic event suggestive of MS.

^s Biological samples may be sent to central laboratory, local laboratory or other academic laboratory and specialized sites for final processing, analysis and reporting due to cell viability and biomarker recovery, such as but not limited to B cell, T cell and innate immune cell subset samples in CSF. Please refer to laboratory manual for details.

^t A PD DNA sample will be collected for patient genotyping (whole genome sequencing; WGS) at the Baseline visit. If the DNA sample is not collected at the baseline visit, it may be collected at any subsequent visit. Collection and submission of this sample is contingent upon the review and approval of the exploratory research by each site's IRB/EC and, if applicable, an appropriate regulatory body. If a site has not been granted approval for WGS sampling, collection of this sample will not be applicable at that site.

^u Adverse events will be reported throughout the study.

^v The primary analysis for this study is event driven, therefore the study duration in the double-blind phase will vary for each patient. In the event that the requisite number of events have accumulated study-wide before the minimum 3-year follow-up, patients will then be unblinded and followed for a minimum of 3 years.

^w Pre-screening MRI scans must include FLAIR sequences to establish whether the individual meets 2017 McDonald criteria for DIS. Pre-screening MRIs will be interpreted by site PIs to determine whether they meet 2017 McDonald criteria for dissemination in space. Individuals established to have RIS in this way must subsequently undergo a full, screening MRI as noted elsewhere.

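### The sample-size figures contradict each other: 33% versus 20% gives about 27% power at 21 events, not the stated 80%

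*Combined protocol and SAP*

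**What the plan says.** Section 6.1 bases the sample size on a two-group comparison of event times at two-sided alpha 0.05. The effect is given as proportions by 4 years: "33% of the patients in the control arm and 20% of patients in the ocrelizumab arm having radiological or clinical evidence of MS". On size and accrual: "This study will enroll approximately 100 patients with an expected recruitment of over 2 years". On events, power and dropout: "A final analysis is based on approximately 21 radiological or clinical events to have 80% power 10% annual dropout rate". Section 4.2.1 sets 1:1 allocation, and Section 6.4.1 makes a stratified log-rank test the primary test.

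The same event count appears elsewhere:

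- Section 3.1 (Description of the Study) gives it as a number: "If the projected number of radiological or clinical events (21) has not been reached when the last patient completes 4 years". In that case "the double-blind phase may be extended until the required number of events have occurred".
- Section 6 (opening text) ties the analysis to both time and events: "The primary analysis will occur when the last randomized patient has reached 4 years and the specified number of new radiological or clinical evidence".
- Appendix 1, footnote v, provides for early accrual, with unblinding to follow: "In the event that the requisite number of events have accumulated study-wide before the minimum 3-year follow-up".
- Section 6.7 (Interim Analyses) uses the event total to decide whether follow-up may be extended after a futility look: "If we are not on target to reach the hypothesized number of events (in the blinded dataset) by the end of the follow-up period". It also allows a superiority look once half the information is available.

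No hazard ratio, formula or derivation is given.

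**The concern.** In a log-rank comparison, power depends almost entirely on the number of events and the hazard ratio. Twenty-one events is a very small number. It gives 80% power only for a very large effect, and 33% versus 20% is a moderate one.

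This calculation is the stated basis for the size of a placebo-controlled trial.

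- **If 20% is intended**, the primary test would miss the planned effect about 7 times in 10, where the plan says 2 in 10. A non-significant result could then be read as evidence against benefit from an adequately powered trial.
- **If a larger effect is intended**, the protocol misstates the effect the trial is sized to detect.

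The unreconciled count also feeds the extension rule in Section 3.1 and the event and information thresholds in Section 6.7.

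**Working it through.** **Inputs.** Section 6.1: 33% and 20% by 4 years, two-sided alpha 0.05, about 100 patients, recruitment over about 2 years, 10% annual dropout, about 21 events, 80% power. Section 4.2.1: 1:1 allocation. Assumed here: proportional hazards throughout and, for expected counts, exponential event and dropout times with uniform 2-year entry.

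**1. Implied hazard ratio.** Hazards per year are −ln(0.67)/4 = 0.1001 and −ln(0.80)/4 = 0.0558. HR = 0.557 and ln HR = −0.5848.

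**2. Attempt to reproduce 80% at 21 events.** Schoenfeld power is Φ(|ln HR|·√(d/4) − 1.96). At d = 21 this is Φ(0.5848 × 2.291 − 1.96) = Φ(−0.62) = 26.8%. Freedman gives 25.6%. Other readings also fall short:

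| Reading | Power at 21 events (or 50 per arm) |
|---|---|
| One-sided alpha 0.05 | 38.0% |
| Risk ratio 0.606 used as HR | 20.8% |
| Odds ratio 0.508 used as HR | 34.2% |
| Two proportions, 50 per arm, two-sided | 31.1% |
| Two proportions, 50 per arm, one-sided | 43.1% |

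The highest value in any combination tried was 76.2%. It took an odds ratio in place of the HR and one-sided alpha 0.20, contrary to the stated alpha.

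**3. Events needed for 80%.**

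- Schoenfeld: 4 × (1.960 + 0.8416)² / 0.5848² = 91.8, so 92.
- Freedman: (1.960 + 0.8416)² × (1.557/0.443)² = 97.07, so 98.

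Nearly all of the 100 patients would need an event.

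**4. Events expected under 33% versus 20%.** Dropout hazard δ = −ln(0.9) = 0.1054. Events per arm are 50 × λ/(λ+δ) × (1 − e^(−(λ+δ)T)).

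- Every patient followed exactly 4 years: 13.65 + 8.22 = 21.9 events; power 27.7%.
- Last patient at 4 years, so follow-up of 4 to 6 years: 25.1 events; power Φ(0.5848 × √(25.1/4) − 1.96) = 31.1%. Entry over 3 years gives 26.5 events and 32.4%.
- No dropout, 4 years each: 50 × (0.33 + 0.20) = 26.5 events; power about 32%.

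**5. Simulation.** An unstratified log-rank test with 100 patients and 20,000 runs gave 25.9% when cut at the 21st event, 27.3% at 4 years each and 30.5% at 4 to 6 years.

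**6. Effect that 21 events could detect.** Schoenfeld: HR = exp(−2 × 2.8016/√21) = 0.294, or 1 − 0.67^0.294 = 11.1% against 33%. Freedman: HR 0.241, or 9.2% against 33%. If the 20% is kept instead, the control proportion would have to be about 53% to 60%.

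**7. What a result would look like.** The critical observed HR is exp(−2 × 1.96/√d): 0.425 at 21 events and 0.457 at 25.1. An observed HR equal to the planned 0.557 would have an approximate 95% CI of 0.24 to 1.31 at 21 events and 0.25 to 1.22 at 25.

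**The case against.** **The analysis is not fixed at 21 events.** Section 6 also requires the last patient to reach 4 years, so 31% at about 25 events describes the planned analysis better than 27%. This is fair, and both figures should be shown. Neither approaches 80%.

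**Proportional hazards is an assumption, and dosing ends at Week 48.** This is also fair. Two non-proportional patterns that keep 33% and 20% at 4 years gave 33% to 37% power at the planned analysis time. Stratifying over four equal strata (assumed) gave 29%.

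**The true event rate may be higher.** The background section cites a 2.7-year median for radiologic progression. Read as the control-arm median at HR 0.557, which is an assumption, it gives about 50 events and 54% power. It would also put about 64% of controls with an event by 4 years (1 − 0.5^(4/2.7)), against the stated 33%.

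**The 20% may be the slip.** With 33% versus 11%, Section 6 timing and the entry assumption above, 20.9 events are expected and Schoenfeld needs 20.6. The fit depends on the formula: Freedman needs 26.0, and simulated power was 76%. The 21 is also close to the 21.9 events expected from 33% versus 20% with 4 years each. So 21 may simply be an expected count to which 80% was wrongly attached. Neither reconstruction can be preferred, and the 33% could itself be the wrong entry.

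**Details are deferred to the SAP.** A later derivation could explain the intent, but it could not make the figures now stated agree.

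**Conclusion.** The contradiction stands. With 33% versus 20%, two-sided alpha 0.05 and 1:1 allocation, power is about 27% at 21 events and about 31% when the last patient reaches 4 years, against the stated 80%. The stated power would need 92 to 98 events; about 22 to 25 are expected.

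The HR of 0.557 rests on proportional hazards. The expected counts rest on exponential times, 10% annual dropout and the entry pattern assumed above. The conclusion does not depend on the choice of formula, and no timing, sidedness or effect-measure reading tried restores 80%. The documents do not establish which entry is in error; only the sponsor can say.

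**What to change.** In Section 6.1, reconcile effect size, event count and power, and state the formula with the accrual, dropout and event-rate assumptions.

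- **If 20% is intended:** replace the 80% with about 27% power at 21 events and about 31% at the planned analysis time. In Section 3.1, keep 21 as a projected count and remove the suggestion that it is the number required for 80% power.
- **If a larger effect was intended:** correct the proportions and state the HR at which 21 events give 80% power, roughly 0.24 to 0.29 depending on the formula. With 33% in the control arm, that means about 9% to 11% on ocrelizumab.

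In either case, name in Section 6.7 the event total behind the projected count and the half-information threshold (21/2 = 10.5, so about 11 events if the total is 21). This last item is clarification; the contradiction does not depend on it.

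The cost is protocol and SAP wording only, with no extra enrolment. Either the stated power becomes less favourable or the stated treatment effect becomes larger.
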